#### **6.4.5.2 MGA012**

The calculated dose will be administered based on the patient's actual weight at Cycle 1 Day 1. Body weights will be measured at Screening and at every dosing visit of each cycle. Significant ( $\geq 10\%$ ) change in body weight from baseline should prompt recalculation of dose. Refer to the Pharmacy Manual for further instructions on allowable parameters for dose rounding of MGA012.

Patients with weight ( $>120$  kg) should be dosed based on Ideal Body Weight (IBW) calculations based on the following formula:

Estimated ideal body weight in (kg):

Males: IBW =  $50 \text{ kg} + 2.3 \text{ kg}$  for each inch over 5 feet.

Females: IBW =  $45.5 \text{ kg} + 2.3 \text{ kg}$  for each inch over 5 feet.

Refer to the Pharmacy Manual for further instructions on allowable parameters for dose rounding of MGD007.

Infusion or allergic reactions may occur with the infusion of monoclonal antibodies and other protein-based therapeutics. Precautions for anaphylaxis should be observed during MGA012

administration. Supportive measures may include, but are not limited to, epinephrine, antihistamines, corticosteroids, IV fluids, vasopressors, oxygen, bronchodilators, diphenhydramine, and acetaminophen. Please refer to **Section 7.2** for specific guidelines regarding the management of infusion reactions. Supportive care measures consistent with optimal patient care will be provided throughout the study according to institutional standards.

#### **6.4.6 Study Drug Preparation and Administration**

Visually inspect parenteral drug products for particulate matter and discoloration prior to administration. Return the vial if solution is cloudy, there is pronounced discoloration (MGD007 drug product solution may have pale-yellow or pale brown color and MGA012 drug product solution may have a pale-yellow color), or there is foreign particulate matter.

Instructions on the preparation of MGD007 and MGA012 are detailed in the Pharmacy Manual.

- Do not mix the study drug with, or administer as an infusion with, other medicinal products.
- **On days that patient receives both MGD007 and MGA012, MGA012 must be administered prior to administration of MGD007.**

##### **6.4.6.1 MGD007**

Administration of MGD007 should begin immediately after preparation of the dosing solution but no later than 4 hours after preparation when stored in the vial at 2° to 8°C (see Pharmacy Manual). If there is a delay in administration of study drug such that it will not be administered on the day of preparation, the Medical Monitor should be notified immediately. Instructions on how to proceed will be provided.

- Administer MGD007 via syringe pump over 120 minutes through an IV line. MGD007 should not be administered as an IV push or bolus.

##### **6.4.6.2 MGA012**

Following dilution [REDACTED] MGA012 will be administered by IV infusion over 60 minutes.

Administration of MGA012 should begin immediately after preparation of the dosing solution but no later than 4 hours after preparation when stored at room temperature (see Pharmacy Manual). [REDACTED]

[REDACTED] If there is a delay in administration of study drug such that it will not be administered according to the

above parameters, the Medical Monitor should be notified immediately. Instructions on how to proceed will be provided.

[REDACTED]

## 6.5 Placebo or Active Comparator

There will be neither placebo nor active control drug for this study.

### 6.5.1 Combination Therapy

MGA012 should be infused *prior to* MGD007 when both study drugs are administered on the same day. After MGA012 infusion, the IV line should be flushed with normal saline infusion given at the same rate as the MGA012 infusion.

**Do not manually push normal saline after MGA012 or MGD007 infusion.**

## 6.6 Treatment Compliance

The study drug will be administered by healthcare professionals under the supervision of the Investigator. Records of dose calculation, administration, and dosing regimen will be accurately maintained by site staff. The monitor will review dose calculation, administration, and regimen, as well as medication accountability during study site visits and at the completion of the study.

## 6.7 Packaging and Labeling

Please see the MGD007 and MGA012 Pharmacy Manuals for detailed information about the packaging of the study drugs. All investigational product will be labeled with a minimum of the protocol number, directions for use, storage conditions; the statements “For clinical trial use only,” and/or “CAUTION: New Drug Limited by Federal (United States) Law to Investigational Use,” and the Sponsor's name and address.

[REDACTED]

[REDACTED]

[REDACTED]

[REDACTED]

## 6.8 Storage and Accountability

Accurate accounting of all study drug must be maintained. The Investigator agrees to keep an inventory of study drugs using the institution's drug accountability logs or logs provided by MacroGenics. Drug disposition records must be kept in compliance with applicable guidelines and regulations.

A Pharmacy Manual will be provided to the Investigator or designee. When the study is completed, copies of all study drug accountability records must be provided to the Sponsor. Original drug accountability records must be maintained with the rest of the documentation for inspection by the study monitors.

[REDACTED]

[REDACTED]

## 6.9 Investigational Product Disposition at End of Study

Upon completion or termination of the study, all unopened vials of study drug must be returned to MacroGenics or its representative, unless the site has received written authorization from MacroGenics to destroy study drug at the site. All drug returns to MacroGenics or its representative must be accompanied by the appropriate documentation and be clearly identified by protocol number and study site number on the outermost shipping container. If MacroGenics approves the destruction of drug at the site, the Investigator must ensure arrangements are made for proper disposal and that appropriate records of disposal are documented and maintained, and copies provided to the Sponsor.

Additional details regarding storage, handling, and accountability can be found in the Pharmacy Manual.

## 7 POTENTIAL ADVERSE EVENTS AND SUPPORTIVE CARE MEASURES

### 7.1 Premedication and Prophylaxis

Clinically significant AEs that may be anticipated based on the mechanisms of action and/or clinical experience to date with MGD007 and/or MGA012 include, but are not limited to gastrointestinal AEs (nausea, vomiting, diarrhea, etc.), infusion related reactions (including CRS), and immune-related AEs. Guidelines for management of these events are provided below in [Sections 7.2 to 7.5](#). In addition, premedication and prophylactic measures described here should be implemented to ameliorate the occurrence and/or severity of gastrointestinal adverse events and infusion-related reaction/CRS.

The supportive care regimen should generally be utilized for all patients being treated with MGD007/MGA012, and will include:

- Dexamethasone (20-mg IV) should be given prior to first dose of MGD007 on Cycle 1.
- Budesonide (9 mg PO daily) starting at 48 hours prior to MGD007 infusion and continuing for 5 days after the MGD007 infusion must be given for at least the first 2 and up to 6 doses of MGD007. Further use of budesonide may be used selectively as indicated in the judgment of the investigator.
- Nonsteroidal supportive care medications will be given prior to first dose of MGD007 on Cycle 1 Day 1 and as clinically indicated post infusion. Use of these medications must be given for the first 6 doses of MGD007 infusion; further use may be given selectively as indicated in the judgment of the investigator. These medications include:
  - Acetaminophen 650 mg PO
  - Diphenhydramine 50 mg IV
  - Ranitidine 50 mg IV or equivalent H2-antagonist
  - Ondansetron 16 mg IV or equivalent antiemetic

Post-infusion:

- IV hydration 500 to 1000cc normal saline administered over 1 to 2 hours post infusion of MGD007 should be considered.
- Monitor for at least 6 hours after each of the following infusions: Cycle 1 Days 1 and 15.
- Inpatient observation for up to 24 hours after initial dose of MGD007 is recommended and may be implemented with subsequent doses of MGD007 at the discretion of the investigator.

### 7.1.1 Rationale for Premedication and Prophylaxis

In addition to 20 mg dexamethasone intravenously (IV) prior to the first dose of MGD007 only, all new patients will receive prophylactic budesonide, an oral non-absorbable corticosteroid, in an attempt to limit the GI toxicities of MGD007 with less systemic immune suppression. This measure focuses on providing budesonide as local steroidal supportive medication within the intestinal tract, to mitigate and control the adverse effects of MGD007 on the GI tract and limit the use of systemic dexamethasone. Limiting systemic corticosteroid use is desirable, in that the immunosuppressive effects of high doses of systemic steroids could interfere with the mechanism of action of MGD007 and MGA012.

Based on preclinical data and the clinical experience noted to date, early management of toxicity will include tocilizumab. Specifically, if Grade 2 or greater vomiting or diarrhea occurs, early management will include tocilizumab (anti-IL6 receptor) at a dose of 8 mg/kg given intravenously. This approach is being deployed to intervene earlier and limit the progression of GI toxicity in patients treated with MGD007 with a less steroid-intensive approach. Repeat dosing of tocilizumab may occur after each MGD007 dosing if required in the judgment of the investigator. Nonetheless, if toxicities are not well controlled with prophylactic oral budesonide and early use of tocilizumab, systemic steroids and/or other measures may be employed as clinically indicated to treat toxicity. Rehydration with oral and/or IV supplemental fluids is also encouraged.

### 7.2 Infusion-Related Reactions Including Cytokine Release Syndrome

The predicted mechanism of action of MGD007 is the creation of an immunological synapse between the tumor target cells bearing gpA33 and immune effectors bearing the T cell specific-CD3 complex, leading to T cell activation and killing of the tumor cell. Activation of T cells can be associated with the production of various cytokines.

**Infusion-related reactions including hypersensitivity/anaphylactic/anaphylactoid reactions or Cytokine Release Syndrome (CRS) may occur. Precautions for the management of these reactions should be observed during MGD007 administration.**

Infusion reactions have also been observed with monoclonal antibodies, including antibodies directed against PD-1 or PD-L1. Infusion reactions (including cytokine release syndrome [CRS]) associated with administration of either MGD007 or MGA012 should be managed according to the standard practice of medicine. General guidelines for the management of such reactions are provided in this section. However, severe reactions may require more intensive interventions (e.g., steroids, anti-TNF $\alpha$  antibodies, and/or IL-6 inhibitors).

Patients should be monitored closely for the development of infusion-related reactions during infusions. Patients must remain in the infusion center for monitoring for at least 6 hours after the infusions on Cycle 1 Days 1 and 15. Medications and supportive measures for the

treatment of severe hypersensitivity reactions should be available for immediate use for an infusion reaction during study drug administration and may include, but are not limited to, subcutaneous (SC) epinephrine (0.3 to 0.5 mL of a 1:1000 solution), antihistamines (e.g., diphenhydramine 25 to 50 mg IV), corticosteroids (e.g., hydrocortisone 25- to 100-mg IV push or equivalent), IV fluids, vasopressors, oxygen, bronchodilators, and antipyretics. Resuscitation equipment and other supplies for the emergency management of an allergic/toxic reaction must be available. The patient should be treated according to the best available local practices and procedures. All supportive measures consistent with optimal patient care will be provided throughout the study according to institutional standards.

Should symptoms of fever or chills develop, it may be difficult to distinguish among potential causes of the symptoms including emerging infection, or infusion reaction. Patients should be evaluated carefully for the presence of infection, with the acquisition of cultures and/or implementation of empiric antibiotic therapy as appropriate based on the assessment of the Investigator. Please refer to [Section 7.2.2](#) for detailed guidance regarding the management of infusion reactions.

## 7.2.1 Grading and Management of Infusion Reactions

Infusion reactions will be categorized as follows:

- Grade 1: mild reaction; infusion interruption not indicated, intervention not indicated; Note: Although interruption in infusion is not indicated, temporary rate reduction is indicated before resuming original rate, as the patient tolerates (see [Section 7.2.2](#))
- Grade 2: therapy or infusion interruption indicated but responds promptly to symptomatic treatment [e.g., antihistamines, non-steroidal anti-inflammatory drugs (NSAIDS), narcotics, IV fluids]; prophylactic medications indicated for ≤ 24 hours
- Grade 3: prolonged (e.g., not rapidly responsive to medication and/or brief interruption of infusion); recurrence of symptoms following initial improvement; hospitalization indicated for clinical sequelae (e.g., renal impairment, pulmonary infiltrates);
- Grade 4: life-threatening consequences; pressor or ventilatory support indicated;
- Grade 5: death.

The above grading scale is the CTCAE v4.03 grading scale for CRS, which is nearly identical to the CTCAE v4.03 grading scale for infusion reaction and allergic reaction and is therefore considered appropriate for grading all infusion reactions in this study, irrespective of the underlying mechanism of the reaction. The Sponsor's Medical Monitor or designee should be contacted immediately if questions arise concerning the grade of the reaction.

## **7.2.2 Management of Observed Infusion Reactions**

All infusion-related reactions should be reported as AESIs and/or SAEs, as applicable.

The following are treatment guidelines (which may be modified as needed by the Investigator according to the best practices of medicine) for infusion reactions. If symptoms of IRR develop follow the guidelines provided in [Table 11](#).

**Table 11 Management of Infusion-Related Reactions**

IRR/CRS (NCI CTCAE v4.03)	Management	Follow-up

Grade 1                      Mild transient reaction, infusion interruption not indicated, intervention not indicated
	
 
• Decrease rate of infusion by 50%.
 
• Monitor for worsening.
 
• Continue rate at 50% reduction and increase dose rate to the original rate by doubling the infusion rate after 30 minutes, as tolerated to the initial rate.
 
	
 
• Monitor closely for worsening symptoms. Educate patient to report worsening immediately.
 
• If worsens: Treat as Grade 2 or 3/4, as appropriate.
 
• Consideration can be given to beginning all subsequent infusions at 50% rate and increasing as tolerated.
 
• Premedication for subsequent dose as recommended (Section 7.1)
 

Grade 2                      Therapy or infusion interruption indicated but responds promptly to symptomatic treatment
	
 
• Stop the infusion if ongoing.
 
• Administer:                             
 
○ Diphenhydramine 50 mg IV
 
○ Ibuprofen 400 mg PO for fever
 
○ Oxygen/bronchodilators/I V fluids
 
 
 
• Resume the infusion at 50% of the prior rate once the infusion reaction has resolved or decreased to Grade 1.
 
• Tocilizumab 8 mg/kg IV may be considered selectively in patients where the event is clearly associated with the administration of MGD007 or occurs prior to the initiation of therapy with MGA012
 
• Consult Medical Monitor.
 
	
 
• Monitor for worsening of symptoms
 
• If worsens or persists after medical intervention: Treat as Grade 3/4 as appropriate
 
• Consideration can be given to beginning all subsequent infusions at 50% rate and increasing as tolerated.
 
• Premedication for subsequent dose as recommended (Section 7.1).
 

**Table 11 Management of Infusion-Related Reactions**

IRR/CRS (NCI CTCAE v4.03)	Management	Follow-up

Grade 3                      Prolonged (not responsive to symptomatic treatment) or recurrence after initial improvement, hospitalization indicated for clinical sequelae.
	
 
• Stop the infusion if ongoing.
 
• Disconnect tubing.
 
• DO NOT FLUSH the tubing.
 
• Administer:                             
 
○ Diphenhydramine 50 mg IV
 
○ Dexamethasone 20 mg IV or methylprednisolone 2-4 mg/kg
 
○ Ibuprofen 400mg PO for fever
 
○ Oxygen/bronchodilators/I V fluids
 
 
 
• Tocilizumab 8 mg/kg IV may be considered selectively in patients where the event is clearly associated with the administration of MGD007 or occurs prior to the initiation of therapy with MGA012
 
• Consult Medical Monitor.
 
• Report as IRE
 
• Report as SAE (if appropriate)
 
	
 
• Monitor for worsening of symptoms
 
• If worsens: Treat as Grade 4
 
• If reaction resolves within 12 hours, then MGA012 can be administered on next scheduled dose.
 
• No further doses of study drugs (MGD007 and MGA012) if a Grade 3 infusion reaction does not resolve within 12 hours despite medical management
 
• Premedication for subsequent dose as recommended (Section 7.1).
 
• Permanently discontinue study drugs (MGD007 and MGA012) if there is a recurrence of Grade 3 reaction at rechallenge.
 

**Table 11 Management of Infusion-Related Reactions**

IRR/CRS (NCI CTCAE v4.03)	Management	Follow-up

Grade 4                      Life threatening consequences, urgent intervention indicated
	
 
• Stop the infusion if ongoing.
 
• Disconnect tubing.
 
• DO NOT FLUSH the tubing.
 
• Administer:                             
 
○ Diphenhydramine 50 mg IV
 
○ Dexamethasone 20 mg IV OR methylprednisolone 2 mg/kg.
 
○ Tocilizumab 8 mg/kg as for Grade 3 events
 
○ Ibuprofen 400 mg PO for fever
 
○ Oxygen/bronchodilators/IV fluids.
 
○ Pressors/Ventilatory support
 
 
 
• Consult Medical Monitor
 
• Report as IRE & SAE
 
	
 
• No further doses of study drugs (MGD007 and MGA012). Permanently discontinue study drugs (MGD007 and MGA012).
 

Grade 5                      Death
	
 
• Report as IRE & SAE
 
	

### 7.3 Management of Diarrhea or Colitis

Based on the respective mechanisms of action, both MGD007 and MGA012 may cause GI side effects that may include diarrhea and/or colitis. Patients should be monitored closely for evidence of diarrhea or other change in bowel habits, as well as other signs and symptoms suggestive of colitis. Clinical observations have shown that MGD007 may cause very early (within 72 hours of drug administration) GI side effects that may include diarrhea, nausea and vomiting. These events can be managed successfully with careful supportive care, as well as prompt recognition and intervention with immune suppression where indicated, including anti-cytokine antibody (tocilizumab) and corticosteroids. Colitis related to checkpoint inhibition with anti PD-1 antibodies is much less common than diarrhea associated with treatment with MGD007, typically does not arise acutely after drug treatment, and is generally treated initially with corticosteroids followed by anti-cytokine therapy (anti-TNF) in patients who fail to respond to corticosteroids. Patients on the present study should be monitored closely for evidence of diarrhea or other change in bowel habits, and patients who develop signs or symptoms including abdominal pain, bloating, nausea, vomiting, and diarrhea with blood in the stools should also be evaluated carefully for potential colitis.

For patients who develop acute GI symptoms prior to the initiation of MGA012 or within 72 hours of treatment with the combination of MGD007 and MGA012 should be treated initially according to MGD007 supportive care principles as outlined below in [Section 7.3.1](#). For

patients who fail to respond to early anti-cytokine therapy within 48 to 72 hours, corticosteroids should be initiated promptly as outlined below. For patients in whom the onset of GI symptoms are over 72 hours after administration of the MGD007/MGA012 combination or in whom signs and symptoms are suggestive of colitis, supportive care should be initiated according to [Section 7.3.2](#), with initial treatment with corticosteroids as outlined below.

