### **7.3.1 Diarrhea Occurring Before Addition of MGA012 to MGD007 or Early (within 72 Hours) After Administration of the MGD007/MGA012 Combination**

- Grade 1 diarrhea - Closely monitor the diarrhea until resolution
- Grade 2 diarrhea:
  - Bowel rest
  - Supplemental IV fluids when necessary with close monitoring of fluid and electrolyte status
  - Tocilizumab (anti IL6 receptor) administered as a single 8 mg/kg IV dose. Repeat dosing of tocilizumab may occur after each MGD007 dosing.
  - Monitoring of frequency of bowel movements and stool guaiac
  - For patients unresponsive to tocilizumab (which should be given first), implementation of additional immune suppression consisting of IV corticosteroids using solumedrol at a dosage of 2 mg/kg/day divided twice daily. As tolerated, patients may be converted to oral corticosteroids (i.e., prednisone 2 mg/kg/day divided twice daily) and tapered as appropriate and guided by the patients' clinical status.
- Grade 3 diarrhea (or Grade 2 diarrhea with blood)
  - Hold both MGD007 and MGA012
  - Hospitalize promptly for further evaluation and management
  - Bowel rest
  - Supplemental IV fluids with close monitoring of fluid and electrolyte status
  - Tocilizumab 8 mg/kg IV
  - Monitoring of frequency of bowel movements and stool guaiac
  - For patients unresponsive to tocilizumab (which should be given first), implementation of additional immune suppression consisting of IV corticosteroids using solumedrol at a dosage of 2 mg/kg/day divided twice daily. As tolerated, patients may be converted to oral corticosteroids (i.e., prednisone 2 mg/kg/day divided twice daily) and tapered as appropriate guided by the patients' clinical status.
  - Stool characterization tests should be performed
  - Imaging to rule out bowel obstruction or perforation

- Consideration of colonoscopy as appropriate
- For patients with severe colitis, or those who do not respond to tocilizumab or corticosteroids, additional immune suppression with anti TNF-alpha antibodies (i.e., infliximab) should be considered early in the course
- For patients with Grade 3 diarrhea that lasts less than 48 hours and responds to medical intervention, treatment may be resumed after resolution of the diarrhea to Grade 1 or less in severity within 14 days.
- Grade 4 diarrhea: discontinue MGD007 and MGA012 and treat as for Grade 3 diarrhea. MGD007 and MGA012 should be permanently discontinued.

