### **7.3.2 Diarrhea with Onset > than 72 Hours After Administration of the Combination of MGD007/MGA012 or Clinical Manifestations Suggestive of Colitis**

- Grade 1 diarrhea - Closely monitor the diarrhea until resolution.
- Grade 2 diarrhea - Increase frequency of monitoring until resolution. For management of symptoms:
  - loperamide/diphenoxylate
  - low-dose steroids if clinically indicated.
  - Consider management as per Grade 3 diarrhea with prolonged Grade 2 event lasting more than 5 to 7 days or relapsed diarrhea.
- Grade 3 diarrhea - Hold both MGD007 and MGA012. Hospitalize patient promptly for further evaluation and management including:
  - Bowel rest
  - Supplemental IV fluids with close monitoring of fluid and electrolyte status.
  - Monitor frequency of bowel movements
  - Consider imaging to rule out bowel obstruction or perforation
  - Consideration of colonoscopy as appropriate
  - Implementation of initial empiric immune suppression consisting of IV corticosteroids using methylprednisolone at a dosage of 2 mg/kg/day (or equivalent) divided twice daily. As tolerated, patients may be converted to oral corticosteroids (i.e., prednisone 2 mg/kg/day divided twice daily) and tapered as appropriate and guided by the patients' clinical status.
  - Taper corticosteroids as clinically indicated

- For patients with severe colitis, or those who do not respond to corticosteroids, additional immune suppression with anti TNF-alpha antibodies (i.e., infliximab) should be considered early in the course.
- May consider restarting MGD007 and MGA012 if it is determined that there is no colitis, or an alternative cause of diarrhea is found, **and** diarrhea resolves to  $\leq$  Grade 1 within 14 days
- Grade 4 diarrhea-discontinue MGD007 and MGA012 and treat as for Grade 3. MGD007 and MGA012 should be permanently discontinued.

If the etiology of the diarrhea is uncertain, tocilizumab administration also can be considered, in the case of Grade 2 or greater diarrhea at the discretion of the Investigator, in consultation with the Sponsor.

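### The 72-hour diarrhea clock in Section 7.3 starts from the MGD007/MGA012 combination, so read literally it sends acute Grade 2 or greater diarrhea after an MGD007-alone infusion to the late-onset branch

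*Protocol*

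**What the plan says.** **Routing.** Section 7.3 uses the early pathway (7.3.1) for acute GI symptoms that start before MGA012 or within 72 hours of the two-drug combination. The late pathway (7.3.2) is for signs suggesting colitis, or as follows: "For patients in whom the onset of GI symptoms are over 72 hours after administration of the MGD007/MGA012 combination". The headings of 7.3.1 and 7.3.2 use the same starting point. None of the three places gives a window for MGD007 given alone once MGA012 has started.

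**Schedule.** MGD007 is weekly and MGA012 is every two weeks from Cycle 1 Day 15 (Section 4.1). The vital-signs entry in Appendix 1 lists Cycle 1 Days 15, 29 and 43 as combined and Days 1, 8, 22, 36 and 50 as MGD007 alone. MGD007-alone visits continue in Cycle 2 and beyond.

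**Rationale.** Section 7.3 states that "MGD007 may cause very early (within 72 hours of drug administration) GI side effects". It describes anti-PD-1 colitis as much less common and typically not acute. Section 7.1.1 adds that "if Grade 2 or greater vomiting or diarrhea occurs, early management will include tocilizumab", with no condition on timing or on which drug was last infused. In 7.3.1, "Repeat dosing of tocilizumab may occur after each MGD007 dosing".

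**The concern.** The 72-hour window exists because MGD007 causes early GI toxicity, yet the clock is tied to a dosing event that happens only every second week. Two sites could read the same text and give different first-line treatment for the same acute event. The difference would depend on whether the last infusion was combined or MGD007 alone.

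On the literal route a Grade 2 event would not get the early tocilizumab that 7.1.1 calls for. A Grade 3 event would get IV corticosteroids first, although 7.1.1 aims to limit systemic steroids because they could interfere with both drugs.

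**Working it through.** The plan gives no figure to reproduce. The check uses the dosing calendar and then compares the two pathways.

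**Inputs.** MGD007 on Days 1, 8, 15, 22, 29, 36, 43 and 50 of each cycle. MGA012 on Days 15, 29 and 43 of Cycle 1, and Days 1, 15, 29 and 43 of later cycles. Dosing visits after Cycle 1 Day 1 have a window of ±1 day (Appendix 1).

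**Step 1: time since the last combined dose.**
- Nominal gap to each MGD007-alone infusion: 7 × 24 = 168 h.
- With ±1 day on both visits: (7 − 2) × 24 = 120 h to (7 + 2) × 24 = 216 h.
- Onset 0 to 72 h after the MGD007-alone infusion: nominally 168 to 168 + 72 = 240 h after the combined dose; with windows, 120 to 216 + 72 = 288 h.
- The smallest value, 120 h, exceeds 72 h, so the literal route is always 7.3.2.
- Days 1 and 8 of Cycle 1 precede MGA012 and go to 7.3.1. Day 22 is the first affected infusion.

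**Step 2: how many infusions.**
- To Day 42: 6 MGD007 doses (Days 1, 8, 15, 22, 29, 36), of which 2 (Days 22 and 36) are MGD007 alone after MGA012 has started.
- Cycle 1 Day 15 to the end of Cycle 2: alone 3 + 4 = 7, combined 3 + 4 = 7, so 7/14 = 50%.

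**Step 3: what changes with the branch.**

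| Grade | 7.3.1 (early) | 7.3.2 (late) |
|---|---|---|
| 1 | Monitor | Monitor |
| 2 | Tocilizumab; IV steroids if unresponsive | Loperamide/diphenoxylate; "low-dose steroids if clinically indicated" |
| 3 | Tocilizumab before IV steroids | IV corticosteroids as initial immune suppression |
| 3, restart | Event under 48 h, responsive to treatment, Grade 1 or less within 14 days | No colitis, or another cause found, and Grade 1 or less within 14 days |
| 4 | Stop both drugs; treat as Grade 3 | Stop both drugs; treat as Grade 3 |

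Only Grade 2 or greater events are affected. The late restart rule is stricter in requiring that colitis be excluded or another cause found, although it has no 48-hour limit.

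**Step 4: consistency within Section 7.** Section 7.4 gives tocilizumab for Grade 2 vomiting without mentioning the combination. After the Day 22 infusion, Grade 2 vomiting would therefore get tocilizumab, while Grade 2 diarrhea on the same day would literally get loperamide/diphenoxylate.

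**Step 5: event rate.** Table 1 of the protocol gives Grade 3 or greater treatment-related diarrhea on weekly MGD007 monotherapy as (1 + 2)/(10 + 11) = 3/21 = 14.3% (exact 95% CI 3.0 to 36.3%). This pools 1 µg/kg, which is above this trial's maximum of 0.8 µg/kg; at 0.8 µg/kg it was 1/10. The table has no Grade 2 count and no rate by dose number, so the share of events affected cannot be calculated.

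**The case against.** The best defense is that combination means the regimen. Section 7.3 contrasts the time before MGA012 with treatment on the combination, and a Day 22 patient is on the combination. Sections 5.4 and 11.1.1 use the word that way. Section 4.1.1 counts DLT time to Day 42 of combined administration, although MGA012 starts only on Day 15. The repeat-tocilizumab line in 7.3.1 also fits this reading. It is plausible and probably what was intended. But 7.3 does not say so, a clock in hours needs a dosing event, and Section 7.5.1.1 counts missed doses of the combination.

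The second defense is that tocilizumab stays available. Section 7.1.1 has no timing condition, and the last line of 7.3.2 allows tocilizumab at Grade 2 or greater when the cause is uncertain, at the Investigator's discretion and in consultation with the Sponsor. Section 7.1 also calls these measures guidelines. All of this stands and limits the consequence. It does not reconcile 7.1.1 with the treatment order in 7.3.2.

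A reader might infer more than the documents support:
- **That half of diarrhea events would be misrouted.** The 7 of 14 counts infusions. In the monkey studies (Section 2.3.3), GI signs came mainly after the first two doses, which here precede MGA012; the first affected infusion is dose 4.
- **That DLT or MTD decisions are biased.** No DLT rule depends on the branch. The exception in 4.2.2 turns on resolution to Grade 1 or less within 7 days with medical therapy, and the documents give no resolution times by treatment.
- **That Table 11 is a conflicting rule.** It covers infusion reactions, and there tocilizumab is only a selective option.

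**Conclusion.** The point holds as a wording inconsistency with a modest safety consequence, and it should be corrected. Read literally, every MGD007-alone infusion from Cycle 1 Day 22 is at least 120 h past the last combined dose, so acute Grade 2 or greater diarrhea after it is routed against the protocol's own rationale.

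This rests on three assumptions: a site applies the wording literally, visits stay within their windows, and there are no overt signs of colitis (which go to 7.3.2 on any reading). On the regimen reading nothing is misrouted. The documents do not support a claim that patients would be denied tocilizumab.

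**What to change.** Change both routing sentences in 7.3 and the headings of 7.3.1 and 7.3.2 so that the clock runs from the most recent MGD007 infusion, whether given alone or with MGA012:
- **To 7.3.1:** diarrhea before MGA012 is started, or with onset within 72 hours of the most recent MGD007 infusion and no signs suggestive of colitis.
- **To 7.3.2:** onset more than 72 hours after the most recent MGD007 infusion once MGA012 has started, or any signs suggestive of colitis.

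Keep the existing prompt move to corticosteroids for patients who "fail to respond to early anti-cytokine therapy within 48 to 72 hours". Patients who switch to MGA012 monotherapy, which Appendix 1 allows after two full cycles, would go to 7.3.2 once 72 hours have passed since their last MGD007 infusion.

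The cost is two sentences and two headings, with no new procedure, data item or analysis. There is one clinical downside. Against the literal reading, the tocilizumab-first window grows from 72/336 = 21% to 72/168 = 43% of the time on both drugs. Some anti-PD-1 diarrhea without colitis signs would then get tocilizumab before steroids. The colitis override and the steroid escalation limit this.
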